Study Protocol, including Statistical Analysis Plan

Official Title:

Does CERC-501 Attenuate Stress-precipitated Smoking Lapse?

Brief Title:

“Does CERC-501 Attenuate Stress-precipitated Smoking Lapse?” ([name], PI)

ClinicalTrials.gov ID: NCT02800928

Protocol Date: Most recent IRB approval—**5/4/18**

Protocol and Statistical Analysis Plan for

“Does CERC-501 Attenuate Stress-precipitated Smoking Lapse?”

(NCT02800928): [name], PI (Yale University)

Scientific Background

There is a significant unmet medical need for treatments that reduce the abuse and dependence of addicting drugs, including tobacco, alcohol, cocaine and opiates. In recent years, opiate antagonists such as naltrexone and nalmefene have been shown to be effective treatments for alcohol and opioid abuse. The effects on tobacco users is equivocal, with well-established effects in short-term laboratory studies of subjective effects, but lack of clear sustained effect on abstinence, perhaps due to the chronic negative effects of mu opioid receptor blockade.

Accumulating evidence indicates that selective antagonism of kappa-opioid receptors (KORs) may provide therapeutic benefit in the treatment of depression. A therapeutic role for KORs in major depressive disorder (MDD) is based upon an emerging scientific literature showing that KORs and the endogenous ligand dynorphin are highly expressed within the prefrontal cortico-striatal loop, which mediates reward and affective states.¹ KOR antagonists have been shown to block stress-induced potentiation of cocaine and conditioned place preference, an animal model of drug relapse.

CERC-501 (previously known as LY2456302) is a high-affinity, selective KOR antagonist being developed for the treatment of substance abuse and MDD, by blocking aversive signaling cascades in the brain triggered by chronic psychological or physical stress.

In a mouse model of precipitated nicotine withdrawal, CERC-501 decreased anxiety-like behavior, somatic signs of withdrawal and hyperalgesia. However, the effects on anxiety and pain behavior had a U-shaped dose response curve, suggesting that doses that selectively block KOR will have the greatest overall effect on symptoms clinically.

In three previous human trials, CERC-501 has been shown to be safe and well tolerated at single oral doses up to 60 mg. At multiple daily doses of 10 mg or less, CERC-501 provides substantial blockade of KOR as assessed in positron emission tomography (PET) imaging studies with minimal effect on mu opiate receptors as assessed by fentanyl-induced miosis.

The current study will evaluate the effect of CERC-501 on the latency to start smoking and the number of cigarettes smoked during the smoking self-administration period after a 18-hour period of abstinence. Subjective measures of cravings, positive and negative mood, and withdrawal symptoms will also be assessed.

Study Objective

The primary objective of this study is to:

To demonstrate that CERC-501 10 mg/day compared to placebo will increase the ability to resist smoking, and reduce subsequent ad-lib smoking following overnight nicotine deprivation and personalized stress imagery in subjects who are heavy smokers.

Study Design and Methods

This is a double-blind, placebo-controlled, two-period, cross-over design examining 10 mg/day CERC-501 compared to placebo in subjects who are cigarette smokers currently not seeking treatment for tobacco use disorder, who currently smoke at least 10 cigarettes per day. Half of the subjects in each group will receive CERC-501 10 mg first in Period 1 and the other half will receive placebo first in Period 1. Each subject will “crossover” to the opposite treatment during Period 2. The crossover design (within-subject analysis) allows the subject to be their own control. Efficacy for CERC-501 on smoking behavior will be assessed in two ways: 1) crossover comparison of CERC-501 10 mg versus placebo; 2) parallel comparison of CERC-501 10 mg versus placebo in Period 1. Gender will be a stratification variable and approximately 50% of the sample will be female.

Sequence 1: CERC-501 10 mg for Period 1 and placebo for Period 2

Sequence 2: Placebo for Period 1 and CERC-501 10 mg for Period 2

After the screening period, subjects will be randomized in a 1:1 manner to one of two sequences (CERC-501 [10 mg] followed by placebo or placebo followed by CERC-501 [10 mg]). Subjects will return to the clinic daily Monday through Friday for supervised study drug administration. On Saturday, Sunday, and holidays the subject will self-administer the study drug. All efforts will be made to have subjects come in for daily medication visits, but if a subject is unable to return for supervised study drug administration, they will be allowed to self-administer the drug. Each period of the crossover treatment consists of a 7-day out-patient treatment period followed by a single in-patient testing day on Day 8. Subjects will participate in a laboratory session following the McKee Smoking Lapse Test² and be discharged from the Hospital Research Unit (HRU) to undergo approximately 7 (+3)-day washout period followed by the second period of the crossover design and approximately 7-day follow up visit.

Each laboratory session will consist of an overnight nicotine deprivation period, followed by personalized imagery (stress). After the imagery procedure, subjects will have the option of initiating a tobacco self-administration session or delaying initiation by 5-minute increments for up to 50 minutes in exchange for monetary compensation. Subsequently, the tobacco self-administration session entails a 1-hour period in which subjects can choose to smoke using a smoking topography system. Primary outcomes measures include the time to the first cigarette

(i.e., ability to resist smoking) and the number of cigarettes smoked. Subjects complete a follow-up appointment (approximately 7 +3 days from the second lab session) to evaluate the durability of effects.

Eligibility Criteria

Inclusion Criteria

1. Provides written informed consent and agrees to complete required clinic visits
2. Male or female 21 to 60 years of age inclusive
3. Body mass index (BMI) 18.5 to 40 kg/m² inclusive
4. Smokes at least 10 cigarettes per day on average for the past 6 months
5. Fagerstrom score ≥3 at screening
6. Currently not seeking smoking cessation therapy
7. Urine dip test for cotinine concentration >150 ng/mL
8. In otherwise good general health without any unstable medical conditions (as determined by medical history, medication history, physical examination, 10- or 12 lead ECG, vital signs, and clinical laboratory testing)
9. Able to read, write, and speak English
10. Females must be either:
 - a. Post-menopausal (amenorrhea for at least 12 consecutive months), surgically sterile -or-
 - b. Women of childbearing potential (WOCBP) must meet the criteria below:
 - i. Uses an acceptable double-barrier method of contraception as determined by the Investigator -and-
 - ii. Is not lactating, has a negative serum beta human chorionic gonadotropin pregnancy test at screening and a negative urine pregnancy test prior to dosing on Days 1 and 8 of each treatment period.
11. Male subjects must agree to use a condom if partner is of childbearing potential

Exclusion Criteria

1. Have used tobacco or other nicotine containing products other than cigarettes (e.g., nicotine patches, pipe, cigars, snuff, chewing tobacco or e-cigarettes) within the past 30 days
2. Any substance use disorder other than nicotine or caffeine as assessed by the Structured Clinical Interview-IV Axis I Disorders (SCID) for Diagnostic³ and Statistical Manual of Mental Disorders (DSM)⁴
3. Current neurological conditions that interfere with study conduct, assessment or treatment in any significant fashion
4. Any lifetime history of bipolar I, II; schizophrenia or any other psychotic disorders; personality disorders, impulse control disorders as assessed by the SCID-IV

5. Current psychiatric conditions that interfere with study conduct, assessment, or treatment in any significant fashion, such as major depressive disorder (MDD), eating disorders, post-traumatic stress disorder, etc. We will screen for worsening of symptoms of depression and/or suicidality at each medication appointment and lab sessions by having participants complete the Beck Depression Inventory (BDI) and the Columbia-Suicide Severity Rating Scale (C-SSRS)⁵. If there is a worsening of symptoms of depression and/or suicidality, the participants will speak a licensed psychologist for evaluation.
6. Recent active or past history of gastric disease such as peptic ulcer disease, gastritis, upper gastrointestinal bleeding, or any gastrointestinal malignancy or precancerous condition
7. Active, comorbid disease that might limit the ability of the subject to participate in the study as determined by the Study MD (i.e., poorly controlled diabetes mellitus, congestive heart failure, etc.)
8. Clinically significant clinical laboratory test taken during screening
9. Elevated aspartate aminotransferase (AST) or alanine aminotransferase (ALT) ≥ 2 times the upper limit of normal (ULN)
10. Human immunodeficiency virus (HIV), Hepatitis B or Hepatitis C positive as determined by serology testing at Screening
11. Positive ethanol breath test at screening or prior to dosing on Days 1 and 8 of each treatment period
12. Positive urine drug test at screening or and/or prior to dosing on Days 1 and 8 of each treatment period except for cannabis
13. History of severe allergies or multiple adverse drug reactions
14. Known hypersensitivity to CERC-501
15. Current use of a proton pump inhibitor or histamine 2 blocker
16. Use of any investigational medication within 2 months prior to the start of this study or scheduled to receive an investigational drug other than the study drug during the course of this study
17. Current use of any psychoactive medications including: antipsychotics, benzodiazepines, mood stabilizers, selective serotonin reuptake inhibitor/serotonin norepinephrine reuptake inhibitor (SSRI/SNRI) or other antidepressants mood stabilizers

Statistical Considerations

PRIMARY AIM 1. Using a double-blind, placebo-controlled parallel-group design, this Phase II study will randomize 20 daily smokers to either 10 mg/day CERC-501 or placebo (n=10 per group). Following titration to steady state levels, we will evaluate medication effects on stress-induced changes in smoking behavior in the laboratory. Primary Hypothesis 1. During the laboratory component, 10 mg/day CERC-501 compared to placebo will increase the ability to resist smoking, and reduce subsequent ad-lib smoking following overnight nicotine deprivation and personalized stress imagery. Linear mixed models with medication condition (10mg/day or

0mg/day) as a within subject factor will be used to evaluate, in turn, time to smoking, and amount smoked collected in the laboratory.

References

1. Carlezon WA, Jr., Beguin C, DiNieri JA, et al. Depressive-like effects of the kappa-opioid receptor agonist salvinorin A on behavior and neurochemistry in rats. *J Pharmacol Exp Ther.* 2006;316(1):440-447.
4. Association AP. *Diagnostic and Statistical Manual of Mental Disorders, 4th Edition (DSM-IV).* Washington DC. 1994.

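### Does the lack of a stated score for subjects who resist for the full 50 minutes leave the time-to-smoking analysis undefined?

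*Combined protocol and SAP*

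**What the plan says.** The analysis of time to smoking takes one sentence. Statistical Considerations, Primary Aim 1, names linear mixed models with medication at two levels (10 mg/day or "0mg/day) as a within subject factor will be used to evaluate, in turn, time to smoking, and amount smoked collected in the laboratory".

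The outcome is described in two earlier places. Scientific Background states: "The current study will evaluate the effect of CERC-501 on the latency to start smoking". Study Design and Methods states "Primary outcomes measures include the time to the first cigarette", and glosses that outcome before naming the second one: "i.e., ability to resist smoking) and the number of cigarettes smoked".

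The procedure is also in Study Design and Methods. After the imagery, a subject may start smoking or choose "delaying initiation by 5-minute increments for up to 50 minutes in exchange for monetary compensation". The next phase is then described: "Subsequently, the tobacco self-administration session entails a 1-hour period in which subjects can choose to smoke using a smoking topography system".

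No section gives a maximum score, a point at which the clock stops, or a censoring or missing-data rule for a subject who delays throughout. The session follows a cited laboratory lapse test, but its scoring is not reproduced.

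**The concern.** A subject who takes every delay step has not smoked by minute 50. The first cigarette then falls somewhere in the 1-hour session, or never. Read literally, a time to first cigarette is unknown at minute 50 and could be as late as minute 110 (50 + 60). Three scores can be imagined:

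- 50;
- the actual clock time, with those who never smoke set to 110;
- missing, because no lapse occurred in the window.

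The same mixed model would then estimate mean minutes resisted within the window, mean time to first cigarette over up to 110 minutes, or a mean among lapsers only. The last would discard the best outcomes. With 20 subjects, a handful of full resisters could move a primary result. If the rule were picked after unblinding, the choice could be steered by the answer.

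**Working it through.** **1. Inputs.** From the documents: steps of 5 minutes, a limit of 50, a 1-hour session, 20 subjects, and 1:1 allocation to two sequences. The documents give no standard deviation, effect size, significance level or share of sessions reaching 50. There is no stated figure to reproduce, and every size below rests on assumptions.

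**2. What the text favours.** Three features point to a score of 0 to 50:

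- The delay option is bounded at 50 minutes.
- The outcome is equated with resisting, which is what the paid window measures.
- The Study Objective and Primary Hypothesis 1 both separate resisting from the ad-lib smoking that comes after it, and each phase has its own primary outcome.

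Running the clock to 110 carries the first outcome into the second phase. Nothing in the text suggests setting the strongest resisters to missing.

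**3. How much the score matters, in closed form.** Let pA and pP be the shares resisting fully on drug and placebo, m the mean time of the others (taken as equal in both conditions), and S the score for full resisters. The mean difference is (pA − pP) × (S − m). Assume pA − pP = 0.20 and m = 15:

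- S = 50: 0.20 × 35 = 7.0 min
- S = 55 (smokes 5 minutes after payment ends): 0.20 × 40 = 8.0 min
- S = 110 (never smokes): 0.20 × 95 = 19.0 min

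Each minute of further abstinence after minute 50 adds 0.20 min. The two rules separate only if full resisters keep abstaining once payment for waiting has stopped.

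**4. Simulation.** 40,000 crossover trials per setting; 10 subjects per sequence; period-adjusted analysis; normal latent delay; within-subject correlation 0.5; true shift 15 min; floor at 0. Placebo mean/SD is 5/20, 25/25, 35/25 and 45/25. The placebo share at the limit is 1 − Φ((50 − mean)/SD); for the last setting this is 1 − Φ(0.2) = 42%. For the running clock, the same latent time is assumed to continue past minute 50.

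| Placebo share at 50 | 1% | 16% | 27% | 42% |
|---|---|---|---|---|
| Drug share at 50 | 7% | 34% | 50% | 66% |
| Estimate, scored 50 (min) | 10.5 | 9.8 | 8.5 | 6.6 |
| Estimate, clock to 110 (min) | 11.0 | 13.5 | 14.3 | 14.5 |
| Power, scored 50 | 82% | 63% | 58% | 49% |
| Power, clock to 110 | 82% | 70% | 71% | 71% |
| Verdicts differ | 2% | 13% | 19% | 28% |

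With no drug effect, each of these two rules, fixed in advance, rejects in 4.8 to 5.1% of trials. Taking whichever of the two is significant rejects in 4.8–5.0, 6.4–6.6, 6.9–7.0 and 7.4–7.5% across the four settings (ranges over two separate runs).

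**5. A different distribution.** Log-normal delays in 5-minute steps (placebo median 10 to 35 min, time ratio 1.5 to 2.0, log-SD 1.0, correlation 0.5) gave differences of 5.5 to 11.2 min scored 50 and 7.4 to 24.2 min with the running clock. Within a setting the ratio of the two ran from 7.39/5.51 = 1.3 to 24.15/9.72 = 2.5, again assuming that latency continues unchanged after minute 50.

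**6. The missing rule.** It gives the most alarming figures: power of 71/28/17/9%, and best-of-three rejection under the null of 6.1/8.9/10.4/9.8%. They show what a poor rule would do, but no reading of this plan leads to it.

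**The case for a change.** The strongest opposing case is that the literal name of the outcome favours a running clock: someone who first smokes at minute 70 did not smoke at minute 50. The drug is hypothesised to lengthen resistance, which would push sessions toward the limit, where the rules diverge most. The cited test may hold the scoring rule, but the plan does not say that it adopts it. Writing the rule down would cost one sentence.

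Part of this stands. The score is not stated, and the cited test cannot fill the gap from these documents. If many subjects reach 50 and keep abstaining, the capped score gives a smaller effect and less power than a running clock: 49% against 71% in the most extreme setting. That is a consequence of measuring resistance in a bounded, paid window, and it does not make the analysis invalid. Minutes resisted within the window is a legitimate target.

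The rest is weaker. The contrast between 50 and 110 depends on latency continuing unchanged after the incentive ends, which the documents do not support. Smoking after minute 50 is also not lost, because the number of cigarettes in the 1-hour session is the other primary outcome. A discrete-time hazard model that censors full resisters at 50 would add little. It too is confined to the window, cannot show any later effect, and has no demonstrated advantage with 20 subjects and two sessions each.

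**Conclusion.** No change is needed. The plan omits a scoring detail, but its own wording leads to a score of 0 to 50 minutes with full resisters at 50. On that reading the linear mixed model estimates the drug-minus-placebo difference in mean minutes resisted within the window, with type I error near 5%. A written rule would record this reading without altering the model or the data. Reporting the share at 50 by condition is something an analyst would do anyway.

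The residual exposure is an after-the-fact choice between 50 and a running clock. Under the assumed normal delays and an unchanged latency after minute 50, that raises false-positive risk from about 5% to at most about 7.5%, and hardly at all if few sessions reach the limit. The conclusion rests on the natural reading of Study Design and Methods and the hypothesis. The documents do not give the share reaching 50, so the size cannot be narrowed further.

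### The only model stated for this two-period crossover has no period term, so a shift between the two laboratory sessions would inflate the standard error of the drug contrast and cost power.

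*Combined protocol and SAP*

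**What the plan says.** Study Design and Methods sets out a "double-blind, placebo-controlled, two-period, cross-over design examining 10 mg/day CERC-501 compared to placebo". It adds that "subjects will be randomized in a 1:1 manner to one of two sequences" and that "Each subject will “crossover” to the opposite treatment during Period 2". Each period ends with the same Day 8 laboratory session: overnight deprivation, personalised stress imagery, then the option of "delaying initiation by 5-minute increments for up to 50 minutes in exchange for monetary compensation", followed by an hour of optional smoking. Two efficacy comparisons are listed without ranking: the crossover contrast and a "parallel comparison of CERC-501 10 mg versus placebo in Period 1". On stratification the section says: "Gender will be a stratification variable and approximately 50% of the sample will be female".

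Statistical Considerations, Primary Aim 1, describes the design differently: "parallel-group design, this Phase II study will randomize 20 daily smokers to either 10 mg/day CERC-501 or placebo (n=10 per group". The analysis sentence in the same paragraph proposes linear mixed models with medication condition (10 or 0 mg/day) "as a within subject factor will be used to evaluate, in turn, time to smoking, and amount smoked collected in the laboratory". Medication is the only term named. No period term appears anywhere, and no model is given for the Period 1 comparison.

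**The concern.** The primary outcome is a behavioural choice, to wait for money or to smoke, which each subject makes twice in the same setting. Familiarity with the task, the payment or the imagery could move the result between sessions whatever the drug does. A period term removes such a shift from the drug contrast. Without one, the shift goes into the residual variance and, if more subjects are lost from one sequence than the other, partly into the drug estimate. With 20 subjects there is little precision to spare.

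Two points in the same text make this harder to resolve. A within-subject medication factor fits only a crossover, yet its paragraph calls the design parallel-group, so the primary analysis is not clearly identified. The Period 1 comparison is between subjects, and the plan does not say whether gender, the stratification variable, enters it.

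**Working it through.** **Inputs from the documents.** Two-period crossover, 1:1 to two sequences; 20 subjects, read as 10 per sequence; medication the only named model term; delay recorded in 5-minute steps up to 50 minutes. The sample size cannot be reproduced, because no alpha, power, effect size or SD is given.

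**Assumptions.** Two-sided 5% test; normal outcome; within-subject SD of 1, so each drug-minus-placebo difference D has variance 2; true effect τ = 0.937, which gives 80% power with period in the model at 10 v 10. The period shift π, in within-subject SDs, is not in the documents and is varied.

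**1. Where the shift goes.** D has mean τ − π in the drug-first sequence and τ + π in the placebo-first sequence. At 10 v 10 the average is τ, so there is no bias.

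**2. Standard error at 10 v 10.**
- With period: √(2/20) = 0.316, on 18 degrees of freedom, for any π.
- Without period: √[(2 + π² × 20/19)/20], on 19 degrees of freedom. At π = 1 this is √(3.053/20) = 0.391.

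Power, type I error and interval width come from 200,000 simulated trials per setting. The test without period is a one-sample t on all differences; the test with period uses the mean of the two sequence means.

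| π | SE without period | Power without | Type I error without | Interval width, without ÷ with |
|---|---|---|---|---|
| 0 | 0.316 | 80.4% | 5.0% | 0.997 |
| 0.25 | 0.321 | 79.2% | 4.7% | 1.014 |
| 0.5 | 0.336 | 76.4% | 3.8% | 1.061 |
| 1 | 0.391 | 64.8% | 1.7% | 1.234 |
| 1.5 | 0.467 | 46.4% | 0.4% | 1.479 |

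With period, power is 80% and type I error 5% in every row. The exact values at π = 0 are 80.24% (19 df) and 80.00% (18 df), so the term costs about 0.2 points when there is no shift.

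**3. Cross-check with fitted mixed models.** Here shifts are scaled by the SD of the difference, and the effect is 0.937/√2 = 0.662. Random-intercept fits gave SEs of 0.252 without and 0.222 with period at a shift of 0.5, and 0.318 and 0.221 at a shift of 1.0, with identical point estimates. In a separate simulation of the differences, power without period was 73% and 50%. These shifts equal 0.5 × √2 = 0.71 and 1.0 × √2 = 1.41 within-subject SDs, and the powers fall between the matching rows above.

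**4. Unequal sequences.** With complete pairs only, the bias without period has size π × |n₂ − n₁|/(n₁ + n₂):
- 9 v 10: 1/19 = 0.05π
- 8 v 10: 2/18 = 0.11π
- 7 v 10: 3/17 = 0.18π

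Type I error at π = 0.5, 1, 1.5 is 4.1%, 2.3%, 1.0% (8 v 10) and 4.5%, 3.1%, 1.8% (7 v 10). If the mixed model keeps Period 1 data from subjects who drop out, the bias is 0.06 to 0.09π (two losses from one sequence) or 0.09 to 0.15π (three), for intraclass correlation 0.01 to 0.7. With period and complete pairs the bias is zero.

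**5. A bounded outcome.** For a delay in 5-minute steps held to 0–50 minutes (assumed latent mean 20, between- and within-subject SD 12, effect 11.6 minutes), power without v with period is 75.3% v 78.6%, 63.4% v 77.5% and 43.4% v 73.8% at shifts of 6, 12 and 18 minutes. Type I error without period is 3.9%, 1.9% and 0.6%; with period it is 5%.

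**6. Gender.** In one simulated 10 v 10 data set with π = 1, the drug contrast was 0.6858 with SE 0.3627 both with and without gender; the SE fell to 0.2577 once period was added. With complete pairs, gender does not affect the crossover contrast. It matters only for the Period 1 comparison.

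**The case against.** - **Silence is not exclusion.** The analysis sentence also omits the random effect, the covariance structure and the degrees of freedom, so a period term may have been intended. That is fair, but none is specified, and a term left unstated can be added or dropped after the results are seen.
- **The harm depends on an assumed shift.** This stands. The 80% baseline is also assumed. The loss is 1 point at 0.25 and 4 points at 0.5; only shifts of 1 or more give large losses, and the documents offer no evidence on size.
- **The main figures are paired-t results, not mixed-model results.** This stands in part. If the subject variance is bounded at zero, power without period at shifts of 1 and 1.5 is about 75% and 65% for intraclass correlation 0.01, 68% and 56% for 0.3, and 65% and 49% for 0.5. A loss remains in each case. At correlation 0.01 with little or no shift, that model's type I error is about 5.9%. The excess comes from bounding the variance and arises with a period term too, but it means the conservative behaviour shown above does not extend to every mixed-model fit.
- **Normality.** The 80% with period holds for a normal outcome only; the bounded-delay check falls to 73.8%. Cigarettes smoked, a count, was not checked.
- **The primary model is obvious.** It sits under Primary Aim 1 and its factor is within-subject, so the crossover reading is much the likelier. The contradictory design label still needs correcting.
- **Gender in the Period 1 comparison has no computation behind it.** True. It rests on gender being the stratification variable.

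**Conclusion.** The concern holds. The plan describes a two-period crossover and specifies no period term in its only model. The main consequence is lost power, of a size the documents do not allow one to fix: from about 1 point at a shift of 0.25 within-subject SDs to about 34 points (80% to 46%) at 1.5, under a normal outcome, 10 per sequence and an assumed 80% baseline, and less when intraclass correlation is low. In the paired-t settings computed with a shift, the test without period is conservative, so inflated false positives are not the worry. Bias is secondary and needs both a shift and unequal sequences. The Period 1 comparison is not affected by a period shift. This should be corrected, but it does not invalidate the design.

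**What to change.** State the primary crossover analysis as a linear mixed model with fixed effects for medication and period and a random subject intercept, fitted to each primary outcome, with the drug contrast taken from it. Reword Primary Aim 1 so that the design label and the 10-per-group statement agree with the crossover, making clear that this model is primary. Separately, state a model for the Period 1 comparison with gender as a covariate.

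The cost is one or two sentences in the SAP and one residual degree of freedom in the within-subject contrast (19 to 18), about 0.2 points of power if there is no shift. No new data, visits or subjects are needed.
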